Generally, primary safety analyses will be based on time from baseline or 30 days after baseline until two months after patients first reached direct bilirubin levels $< 2\text{mg/dL}$. Baseline will be defined as information collected at the date that treatment starts for Omegaven[®] patients and on the date that patient reached bilirubin levels > 2 for soybean oil fat emulsion patients. Information on mortality and transplant will be collected during the whole treatment with Omegaven[®] and during the whole period for which we have data available in the Andorsky et al. dataset. Primary efficacy analysis will include time from baseline until the patient normalizes bilirubin (presents three consecutive direct bilirubin $\leq 2\text{ mg/dL}$ or a direct bilirubin $\leq 2\text{ mg/dL}$ and weaned from TPN). With exploratory purpose, we will also describe the curve of the several markers for the entire period that Andorsky et al. recorded data.

Outcome/Endpoints

1. Treatment safety

Our primary outcome for treatment safety will be based on patient's essential fatty acid profile. We will compare patients before treatment with Omegaven[®] started and after treatment started (one month after treatment started until treatment stopped) with respect to the frequency with which triene/tetraene ratio > 0.2 at any time. We will also compare the occurrence any event of of hypertriglyceridemia (serum triglyceride $> 400\text{mg/dL}$) between Omegaven[®] and soybean oil fat emulsions. Primary analyses for these and all other safety outcomes will be based on a follow-up time for Omegaven[®] and soybean oil fat emulsions starting 30 days after baseline, i.e., 30 days after treatment started for Omegaven[®] patients and 2 months after the first direct bilirubin level $< 2\text{ mg/dL}$ was recorded. We will also explore comparisons including the time from baseline until the end of follow-up period.

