Additional comparisons across treatment periods for subjects receiving Omegaven® will be aimed to assess occurrence of spontaneous bleeding (e.g., unexplained bruising, oozing from gums/incision sites), and maximum triene/tetraene ratio, minimum platelets, and maximum international normalized ratio (INR), trends in pre-albumin (age standardized levels). We will also explore trends in coagulopathies based on curves of platelets, prothrombin time (PT), partial thromboplastin time (PTT) over time, and INR. We will also describe the rate with which INR ratios were > 2 (number of days/follow-up time), as a marker of coagulopathies.

Additional comparisons between Omegaven® and soybean oil fat emulsion groups will be performed with regards to rate in which albumin is > 3 g/dL, maximum triglyceride level, rate of blood stream infections (number of positive blood cultures/follow-up-time under PN after baseline), rate of central venous catheter (CVC) infections (number of CVC infections/follow-up time and number of gram positive CVC infections/follow-up time), and occurrence of anaphylactic reactions after baseline.

Nutritional outcomes between Omegaven® and soybean oil fat emulsion groups that will be compared include changes in weight- and height-for-age Z-scores from baseline to 10% PN or cessation of PN..

We will describe trends over time for all outcomes associated with fatty acid profiles (including triene/tetraene ratios, triglycerides, total omega-6 fatty acids, total omega-3 fatty acids, total saturated, total monounsaturated, and total polysaturated fatty acids). Specific fatty acids such as arachidonic, palmoleic, palmitic, oleic, stearic, and linoleic fatty acids will also be evaluated and described. Also, for exploratory purposes, we will compare the trend in weight- and height-for-age Z-scores between both groups.

2. Omegaven®

3. The patient will complete treatment with Omegaven® in this study when he/she is completely off PN, develops a contraindication for further use, or the patient/family requests to be removed from the study.

f. Data Collection Methods, Assessments and Schedule

Omega-3 Fat Emulsion (Omegaven™)

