Analysis of Baseline Characteristics

For statistical purposes, baseline values will be defined as the last measurement before starting to administer Omegaven® for patients, in the treatment group, and as the measurement taken when a patient first had a direct bilirubin level > 2 mg/dL recorded, in the historical control group. Descriptive statistics for all baseline relevant risk factors will be summarized for Omegaven® (omega-3 based fat emulsion) and historical control (soybean oil fat emulsion) groups. Associations between categorical predictors and Omegaven® vs. soybean oil fat emulsion groups will be tested through chi-square tests. Associations between continuous predictors and treatment groups will be studied through means (and standard deviations) and t-tests, or medians (and interquartile ranges) and Wilcoxon tests, when appropriate.

Analysis of Safety and Tolerability of Omegaven®

All primary safety and tolerability analyses will be based on descriptive statistics. In secondary analyses, we will also assess the statistical significance of differences. Some safety and tolerability outcomes will be measured only in the Omegaven® group. For those, we will compare results before starting PN with Omegaven® (while receiving PN with soybean oil fat emulsions) with after starting PN with Omegaven®. The period receiving Omegaven® will start to be counted 30 days after beginning PN with Omegaven® for the main analysis. Outcomes measured in the Omegaven® and soybean oil fat emulsion groups will be described separately for each of those groups for a period starting 30 days after baseline, i.e., 30 days after starting PN with Omegaven®, for the treatment group, and 30 days after bilirubin > 2 mg/dL, for the soybean oil fat emulsion group.

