Primary outcomes measured only in the Omegaven® group will include whether the triene/tetraene ratio was ever > 0.2 during the intervention period and whether the INR was ever > 2. Secondary outcomes measured only on the Omegaven® group will include platelets, prothrombin time (PT), partial thromboplastin time (PTT), and other components of the fatty acid profile. Analysis of all categorical outcomes will be based on proportions and of all continuous outcomes will be based on means or medians of the individual mean, maximum or minimum values, as appropriate, during the respective follow-up period. Comparisons between periods (pre and post-treatment) will be performed based on paired tests, parametric or non-parametric, as appropriate. We will also explore trends over time (e.g., decreasing for INR and increasing for pre-albumin) and estimate p-values via regression models using generalized estimating equations or random effects to account for within subject correlations. When describing outcomes over time, we will explore the effect of predictors of poor hepatic outcomes, such as use of antifungal agents (e.g., amphotericin) and antidiarrheal agents (e.g., loperamide), on potential spikes.

Primary outcomes measured in the Omegaven® and soybean based fat emulsion groups will include whether triglycerides were ever > 400mg/dL, whether albumin was ever > 3, any occurrence of unexpected bleeding and number of times it occurred, occurrence of any anaphylactic reaction, rate of blood stream infections as shown by positive blood cultures, rate of line infections and gram positive central venous catheter infections. Outcomes will be summarized for each study group based proportions, poisson rates, mean, minimum, or maximum over the subject follow-up period, and statistical significance of differences between groups will be estimated with exploratory purpose via Fisher's exact test, Wilcoxon or t-tests, as appropriate.

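### Scoring albumin as ever above 3 lets one good value settle a primary safety outcome: it is insensitive to later falls, rises with the number of samples, and conflicts with the rate named in the endpoint section

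*Combined protocol and SAP*

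**What the plan says.** Section 5c, Analysis of Safety and Tolerability, lists the primary safety outcomes measured in both groups. Among them is "whether albumin was ever > 3". The other items are harms: "whether triglycerides were ever > 400mg/dL", unexpected bleeding, anaphylactic reaction, and blood stream and line infections. The Omegaven-only list has the same pattern, for example "whether the INR was ever > 2".

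On summaries, the same section states "Analysis of all categorical outcomes will be based on proportions". For the two-group outcomes it adds "Outcomes will be summarized for each study group based proportions, poisson rates, mean, minimum, or maximum over the subject follow-up period", without saying which summary belongs to albumin.

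Section e (Definition of Primary and Secondary Outcomes/Endpoints), under Treatment safety, gives albumin differently: a "rate in which albumin is > 3 g/dL", placed among the additional comparisons between groups.

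The safety window is described "for a period starting 30 days after baseline" (section 5c) and runs "until two months after patients first reached direct bilirubin levels" below 2 mg/dL (section e).

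**The concern.** For a harm, scoring any occurrence is a sensible screen because one bad value flags the patient. Applied to a favourable state, the same rule works in reverse: one good value clears the patient, and nothing later can change the score. A patient whose albumin starts above 3 and then deteriorates is counted with one whose albumin never moved.

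The chance of at least one value above 3 also grows with each sample taken. The window closes on bilirubin response, so its length varies by patient and, if hypothesis 2.1 is right, by group. Sampling differs too. Table 3 suggests weekly albumin on Omegaven until direct bilirubin falls below 2, then monthly. Section f says the first historical cohort was abstracted every two weeks. The limitations section expects more missing data in controls. A proportion that depends on sample count can therefore differ between groups with no difference in albumin.

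Finally, the two sections name different quantities at different ranks, so an analyst cannot follow both.

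**Working it through.** The plan states no albumin mean, SD, event rate or power, so there is no figure of its own to reproduce. All albumin values below are assumptions.

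**One patient.** Albumin falls evenly from 3.4 to 2.0 g/dL over 17 samples, in steps of 1.4/16 = 0.0875. The first five values (3.40, 3.31, 3.23, 3.14, 3.05) exceed 3. The score is yes, the same as for a patient who stays at 3.4. The share above 3 is 5/17 = 29% and the lowest value is 2.0; both show the fall.

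**Model.** Sample j in a patient has mean m_j plus a patient effect b with SD 0.3 and within-patient error with SD 0.3.

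- Given b, p_j(b) = Φ((m_j + b − 3)/0.3).
- P(ever > 3) = average over b of 1 − ∏(1 − p_j(b)).
- Expected share above 3 = average over j of Φ((m_j − 3)/√(0.3² + 0.3²)), where the root is 0.424.

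**Sensitivity to a fall (12 samples).**

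| Start | Course | Ever > 3 | Share of samples > 3 |
|---|---|---|---|
| 3.4 | stable | 99.6% | 83% |
| 3.4 | falls to 2.2 | 95% | 37% |
| 3.0 | stable | 92% | 50% |
| 3.0 | falls to 2.2 | 75% | 21% |
| 2.8 | stable | 80% | 32% |
| 2.8 | falls to 2.2 | 59% | 14% |

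In every falling row the last value has mean 2.2, and Φ(0.8/0.424) = 97% of patients end below 3. Starting from 3.4, the outcome moves by about 5 points while the share moves by 83 − 37 = 46.

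**Dependence on sample count (no change in albumin).**

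| Stable mean | 6 samples | 12 | 24 | Share > 3, any count |
|---|---|---|---|---|
| 2.4 | 27% | 37% | 48% | 8% |
| 2.8 | 69% | 80% | 87% | 32% |
| 3.4 | 98.7% | 99.6% | 99.9% | 83% |

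The share column does not involve the count; at 2.8 it is Φ(−0.2/0.424) = 32%.

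**Other assumptions.** With between-patient SD 0.4 and 17 samples, a 1.0 g/dL fall from 3.4 moves ever-above-3 from 99% to 93%, and the share from 79% to 43%. Over 16 weeks, two-weekly sampling gives 16/2 + 1 = 9 values and weekly gives 16 + 1 = 17. At a stable mean of 2.8 with SDs 0.4 and 0.3, those counts give 71% and 78%. If samples were independent with a 5% to 10% chance each of exceeding 3, 1 − (1 − p)^k gives 37% against 58%, and 61% against 83%. With 30 patients per group, Fisher's test would then reach p ≤ 0.05 in 29% to 38% of studies with identical albumin. Independence exaggerates the effect of sample count, so this is the unfavourable end.

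**The case against.** Four points on the other side have force.

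- **The outcome is not blind.** A reader might infer that it can never show a fall. The documents do not support that: the window opens at day 30, so a fall below 3 by then that persists scores no. When patients start near or below 3, falls are visible: 92 − 75 = 17 points from 3.0, and 80 − 59 = 21 points from 2.8. From 2.8 the share moves by 32 − 14 = 18 points, so it is no more sensitive there. Likewise, saturation near 100% is a feature of high albumin, not a general property; at a mean of 2.4 the outcome is 27% to 48%.
- **Section e already names a rate.** A rate over follow-up would register a fall and need not rise with sampling. Section 5c also lists minimum and mean among possible summaries. Neither is assigned to albumin, however, and section 5c still names the ever-above-3 form as the primary outcome.
- **A favourable state is a legitimate thing to score.** Both sections use the > 3 direction, so the sign is not a slip. What fails as a safety measure is joining that direction to a single qualifying value.
- **The consequences are limited.** Section 5c makes primary safety analyses descriptive and between-group tests exploratory. No decision rule hangs on albumin.

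A reader might also infer that the definition favours Omegaven. The documents do not fix this: faster bilirubin response would shorten Omegaven windows and favour controls, while weekly sampling and fewer missing values point the other way.

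**Conclusion.** The point holds in limited form. As section 5c words it, the albumin outcome is insensitive to later falls, most of all in patients who start above 3, and it rises with the number of samples. Section e gives a different quantity at a lower rank, so the two must be reconciled.

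The sizes rest on assumed means, SDs and sample counts. That the score cannot fall after one value above 3, and that its probability rises with sampling, does not depend on them. The wording problem is therefore certain; the magnitude is not. The harm is a safety description that could look reassuring, or show a group difference, for reasons unrelated to albumin. It is not a failed confirmatory test, because the plan has none here. It should be changed before analysis.

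**What to change.** In both section e and section 5c, replace the ever-above-3 score with the share of follow-up time with albumin below the plan's own 3 g/dL cut, or the share of fixed-interval values below it on the same grid in both groups. State which side a value of exactly 3 falls.

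Add the lowest albumin as a supporting summary. The minimum also depends on how many samples are taken, so a common window alone is not enough; take it from the same grid and window in both groups. The grid can be no finer than the sparsest source. Omegaven sampling drops to monthly once bilirubin falls and the first control cohort is two-weekly, so monthly values are a natural choice. Check the spacing in the 1999–2004 cohort, which the plan does not state. Report the number of available values per patient by group.

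Give the outcome the same rank in both sections. The cost is wording: albumin is already on the Table 3 schedule, and the plan already commits to comparing it between groups.

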Children requiring prolonged courses of PN are at risk for developing PN associated liver disease. We hypothesize that although omega-6 fatty acid emulsions prevent fatty acid deficiency, they are not cleared in a manner similar to enteral chylomicrons and therefore accumulate in the liver and resulting in steatotic liver injury. We further hypothesize that a fat emulsion comprised of omega-3 fatty acids (i.e., fish oil) such as Omegaven® would be beneficial in the management of steatotic liver injury by its inhibition of de novo lipogenesis, the reduction of arachidonic acid-derived inflammatory mediators, prevention of essential fatty acid deficiency through the presence of small amounts of arachidonic acid, and improved clearance of lipids from the serum. Animal studies have shown that IV fat emulsions (IFE) such as fish oil that are high in eicosapentaenoic and docosahexaenoic acid reduce impairment of bile flow which is seen in cholestasis caused by conventional fat emulsions. Furthermore, we hypothesize that that intravenous omega three fatty acids will be well tolerated and might reduce the inflammatory effect in the liver of prolonged PN exposure and could potentially reverse any hepatic dysfunction due to PN/IFE use. By administering Omegaven® in place of conventional phytosterol/soybean fat emulsions we may reverse or prevent the progression of PN associated cholestasis and thus allow the patient to be maintained on adequate PN until they are able to ingest adequate nutrition enterally.

1. Specific Aims /Objectives

1. To determine the safety profile of an intravenous omega-3 fat emulsion (Omegaven®)

Hypothesis for Aim 1:

1.1 – After starting Omegaven® on PN, the rate of fatty acid deficiencies and imbalances will be as low as before Omegaven®. Also, the rate of triglyceride events > 400 mg/dL with Omegaven® will be similar to that seen with PN administered with soy oil IFE (conventional emulsion, i.e., Intralipid®).

1.2 – PN containing Omegaven® will be safe for patients with respect to the risk of unexpected bleeding, coagulopathies, and other adverse events.

1.3 – PN containing Omegaven® will promote more short-term growth and development than conventional fat emulsions.

2. To determine if established PN associated liver disease can be reversed or its progression halted by using a parenteral fat emulsion prepared from fish oil as measured by normalization of serum levels of hepatic enzymes and bilirubin.

Hypothesis for Aim 2:

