- a) The patient will be PN dependent and at risk for significant hepatic injury due to prolonged use of parenteral nutrition.
- b) Have significant hepatic dysfunction due to parenteral nutrition despite utilization of all conventional therapies.

Inclusion Criteria:

1. Patients will be PN dependent (unable to meet nutritional needs solely by enteral nutrition) and are expected to require PN for at least another 30 days
2. Patients considered eligible for study participation must have parenteral nutrition associated liver disease (PNALD) as defined as a direct bilirubin of ≥ 2 mg/dl or currently on Omegaven through another protocol. Other causes of liver disease should be excluded. A liver biopsy is not necessary for treatment.
3. Direct bilirubin > 2.0 mg/dl, or already on Omegaven through another protocol.
4. Signed patient informed consent.
5. The patient must have utilized standard therapies to prevent the progression of his/her liver disease including surgical treatment, cyclic PN, avoiding overfeeding, reduction/removal of copper and manganese from PN, advancement of enteral feeding, and the use of ursodiol (i.e., Actigall[®]).

Exclusion Criteria:

1. Pregnancy
2. Other causes of chronic liver disease (Hepatitis C, biliary atresia, and alpha 1 anti-trypsin deficiency,)
3. Enrollment in any other clinical trial involving an investigational agent (unless approved by the designated physicians on the multidisciplinary team)
4. The parent or guardian or child unwilling to provide consent or assent

In rare instances, patients diagnosed with PNALD may later be found to have liver disease due to other causes in addition to the use of PN (i.e., inborn errors of metabolism, viral infections). Such causes may not be known at the time of enrollment and will not preclude them from continuing in the study. For the sake of statistical analysis, however, these patients will be excluded although all data will be collected and reviewed.

Screening Procedures

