We will also compare nutritional outcomes of the two groups including difference in weight-for- age Z-scores and height-for-age Z-scores from baseline to the moment in which the child starts enteral feeding and to the moment in which the child receives less than 10% of their calories from PN. Comparison between study groups will be performed via t-test or Wilcoxon tests, as appropriate. Using linear regression, we will explore adjustment for baseline alternative predictors of interest. Trends over time in Z-scores will also be explored using regression with repeated measure methods.

Analysis of Efficacy of Omegaven®

The primary outcome to gain preliminary evidence of efficacy will be based on the time from baseline to normalization of bilirubin level, i.e, first time point among three consecutive in which bilirubin is < 2 mg/dL. We do not anticipate that any subject will present a rebound on direct bilirubin after normalization. However, we will describe the cohort with respect to the frequency of rebounds in bilirubin levels.

Crude comparisons of time to normalize direct bilirubin levels between Omegaven® and soybean oil fat emulsion patients will be based on Kaplan-Meier curves and log-rank tests. We will estimate hazard ratios and adjust for potential baseline confounders using Cox-proportional hazard models. For all survival analysis based on non-parametric or semi-parametric methods, we will attribute an infinite time to event (i.e., time to event larger than the largest follow-up time in the whole study population) for subjects who die or receive a liver transplant before bilirubin is normalized. Subjects who die before their bilirubin levels normalize (particularly due to liver failure) have in fact the worse outcome (infinite time to normalize bilirubin) and were not censored before reaching the endpoint of interest. Results of these analysis will be compared with results of analysis excluding subjects who die or are transplanted. Time to reach a total bilirubin of 1.2 will also be compared using survival analysis methods. Analysis of this outcome will proceed as described for direct bilirubin.

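### Growth is defined differently in two places, and the planned test ignores how long each child took to reach the feeding milestone

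*Combined protocol and SAP*

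**What the plan says.** - **Specific Aims, hypothesis 1.3:** PN with Omegaven "will promote more short-term growth and development than conventional fat emulsions". No time horizon, effect size or standard deviation is given.
- **Definition of Primary and Secondary Outcomes/Endpoints, item 1 (Treatment safety):** the groups are compared on "changes in weight- and height-for-age Z-scores from baseline to 10% PN or cessation of PN". A comparison of Z-score trends is added as exploratory.
- **Data Analysis Plan (section 5c), Analysis of Safety and Tolerability:** the Z-score difference is taken "from baseline to the moment in which the child starts enteral feeding". A second difference ends when PN supplies under 10% of calories. Groups are compared by t-test or Wilcoxon test. Linear regression on baseline predictors and repeated-measures trends are to be explored.
- **Inclusion Criteria, Omegaven group:** criterion 1 reads "Patients will be PN dependent (unable to meet nutritional needs solely by enteral nutrition"), and criterion 5 lists "advancement of enteral feeding" among the standard therapies that must already have been used.
- **Safety windows:** the outcomes section says "Primary analyses for these and all other safety outcomes will be based on a follow-up time" that begins 30 days after baseline. The Data Analysis Plan describes two-group safety outcomes "for a period starting 30 days after baseline". Growth is listed under safety but is counted from baseline.

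**The concern.** The outcome behind hypothesis 1.3 has two definitions and no ranking between them, so the choice could be made after the data are seen. One end point may lie before baseline for some children, and no rule says what their change score then is. The remaining end points are dates set by the child's own course after baseline. A Z-score standardises for age but not for length of observation. Two children with the same monthly drift therefore get different change scores if one is weaned sooner. A two-sample test on those scores mixes rate of growth with time on PN. A child who dies, is transplanted or stays on PN has no value at the milestone, and the growth plan does not say what happens to that child.

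**Working it through.** The documents give no power, effect size or standard deviation for growth, so there is no growth figure to reproduce. The check compares the sections and then illustrates the effect of unequal intervals.

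**1. The two definitions**

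| End point | Outcomes section | Data Analysis Plan |
|---|---|---|
| Start of enteral feeding | absent | yes |
| 10% PN | yes | yes (below 10% of calories) |
| Cessation of PN | yes | absent |

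Cessation of PN is also unclear in itself: Duration of Therapy allows Omegaven to continue after the dextrose and protein part has stopped.

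**2. Can enteral feeding start before baseline?** Criterion 1 excludes only children who live wholly on enteral nutrition, so partial feeding is allowed. Criterion 5 requires that enteral feeds were already being advanced. For such a child in the Omegaven group the interval is zero or negative. For controls the inference is weaker. The 1999-2004 cohort's criteria say only that prior therapies may include advancing feeds, and the first historical cohort has no such criterion.

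If a share f of each group is given a zero interval, a true difference of 0.5 Z (assumed) shrinks to 0.5 × (1 − f). That is 0.375, 0.25 and 0.125 for f = 25%, 50% and 75%. The documents give no value for f.

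**3. Could durations differ between groups?** The documents give no durations, but the groups are set up differently. Baseline is treatment start for Omegaven and the first bilirubin above 2 mg/dL for controls. The first control cohort needed at least 90 days of PN dependence, whereas Omegaven patients need an expected further 30 days. The protocol expects Omegaven patients to have more severe liver disease.

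**4. What unequal durations do.** Let both groups have the same Z-score slope s per month and mean times T₁ and T₂ to the milestone. Then

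false difference = s × (T₂ − T₁).

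The slopes and times below are assumptions. The simulation (20,000 runs) uses 25 children per group, a size taken from the adverse-event power tables. It also assumes gamma-distributed times, a slope SD of 0.06 per month and a residual SD of 0.5.

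| s (Z/month) | Mean months | False difference | Rejection at nominal 5% |
|---|---|---|---|
| 0.05 | 3 vs 6 | 0.05 × 3 = 0.15 | about 13% |
| 0.05 | 4 vs 8 | 0.05 × 4 = 0.20 | about 17% |
| 0.10 | 3 vs 6 | 0.10 × 3 = 0.30 | about 36% |
| 0.10 | 4 vs 8 | 0.10 × 4 = 0.40 | about 47% |
| 0 | 3 vs 6 or 4 vs 8 | 0 | about 5% |
| any of these | 4 vs 4 | 0 | about 5% |

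Measured at a fixed 3 months, the difference is 0 and rejection about 5% in every row. A negative slope gives the same sizes with the opposite sign. The rejection rates depend on the assumed spread. With an SD of change of 0.8 to 1.0 and a normal approximation, they are about 8% to 10% for 0.15 Z and 29% to 42% for 0.40 Z.

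**5. Existing safeguards.** The optional regression covers baseline predictors, not interval length. The plan gives rules for death and transplant in the bilirubin survival analysis and the liver-marker trends, but none for growth.

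**The case against.** The strongest reply is that the plan already contains much of the remedy: both sections foresee Z-score trends over time, which do not depend on a milestone. That stands, and it makes the fix cheap. But the trends are exploratory, with no stated model or horizon, and the t-test or Wilcoxon comparison remains the main one.

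A second reply is that Z-scores already account for age. This is right as far as it goes: with no drift, or with equal durations, there is no bias. But if hypothesis 1.3 is true, the two groups' slopes differ, so at least one is not zero and duration matters.

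A third is that start of enteral feeding may be loose wording for the switch from PN to enteral nutrition. If so, the before-baseline problem largely disappears. The text does not settle it, and the wording still needs correcting.

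A fourth is that measuring to the end of PN keeps observation on treatment, which suits a hypothesis about PN containing Omegaven. That is defensible, provided that interval length is accounted for.

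A reader might also infer more than the documents support:

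- **That many patients have already passed the enteral-feeding point at entry.** No count is given, and the inference is weak for controls.
- **That the group observed longer is favoured.** This holds only if Z-scores rise during PN. If they fall, that group is penalised.
- **That the plan excludes the sickest children.** It is silent on them, which is a different fault.
- **That the bias has a known size.** Stretching the example to 3 vs 9 months at 0.10 Z per month gives 0.10 × 6 = 0.60 Z, but no slope or duration comes from the documents.

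**Conclusion.** The concern holds within limits. The definitions differ between sections. One end point can precede baseline, at least in the Omegaven group. The main test compares changes over intervals that depend on each child's course, with no term for their length and no rule for children who never reach the milestone. Bias needs two conditions: drift in mean Z-scores during PN, and a difference between groups in time to the milestone. Neither can be checked from the documents, so size and direction are unknown; 0.15 to 0.40 Z is an illustration under the stated assumptions.

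The stakes are moderate. Growth is not among the primary safety outcomes listed in the Data Analysis Plan, primary safety analyses are descriptive, and the primary bilirubin analysis is untouched. But hypothesis 1.3 is a stated superiority claim that rests on this comparison, so the plan should be changed.

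**What to change.** 1. Reconcile the outcomes section and the Data Analysis Plan on one growth definition, and say what counts as cessation of PN. State that growth runs from baseline, as an exception to the 30-day start for other safety outcomes.
2. Drop start of enteral feeding as a growth end point.
3. Make the repeated-measures analysis the main growth analysis: a mixed model of Z-score on time from baseline by group, using all available measurements and adjusted for baseline Z-score. Report the group contrast at a stated short-term horizon, for example 12 weeks, where control data allow.
4. State how death, transplant and never reaching 10% PN are handled, and report their numbers by group. A fixed horizon does not settle this by itself, because a child who dies earlier has no value there.
5. Keep change to below 10% PN as descriptive, always shown with its duration.

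The cost is mainly wording, since serial Z-scores are already intended. Growth indices are monitored in the Omegaven group, and the first control cohort was abstracted at two-week intervals, with birth dates to be obtained.

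There are two downsides. Control weights and lengths may be sparse at fixed times: the documents do not show that lengths exist at given weeks, and they expect more missing data in controls. Later time points will also include growth after weaning for some children, so the horizon should be short and the share still on PN at that time reported.
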